10.3 Follow-up for toxicities

All subjects must be followed up for safety (adverse events and serious adverse events) for 30 days following the last dose of study treatment (trametinib).

Subjects whose treatment is interrupted or permanently discontinued due to an adverse event or a clinically significant laboratory value must be followed until resolution or stabilization of the event, whichever comes first. Further guidelines and recommendations for the management of specific study treatment induced toxicities are provided below.

10.4 Criteria for Removal from Protocol Therapy and Off Study Criteria

10.4.1 Criteria for Removal from Protocol Therapy

- a) Intolerable toxicity (leading to treatment interruption >4 weeks)
- b) Worsening disease at any time at the discretion of the investigator
- c) Refusal or withdraw of consent for further protocol therapy by parent/guardian/LAR or subject
- d) Physician determines it is in subject's best interest
- e) Completion of planned therapy
- f) Non-compliance with protocol requirements (e.g., unexcused missing more than one scheduled study visit or missing > 15% of doses of study drug)

Subjects who are off protocol therapy are to be followed (as indicated) until they meet the criteria for Off Study (see below). For subjects who withdrawal due to AE, the medical condition will be tracked for at least a month after discontinuing the study drug or until resolution of the AE.

Follow-up data will be required until one of the following off study criteria is met.

10.4.2 Off Study Criteria

- a) Death
- b) Lost to follow-up
- c) Withdrawal of consent for any further follow up data submission
- d) Completion of protocol defined follow-up period.

10.5 Adverse Reporting Requirements

10.5.1 Clinical Adverse Events

Clinical adverse events (AEs) will be monitored throughout the study.

10.5.2 Definition of an Adverse Event

An adverse event is any untoward medical occurrence in a subject who has received an intervention (drug, biologic, or other intervention). The occurrence does not necessarily have to have a causal relationship with the treatment. An AE can therefore be any unfavorable or unintended sign (including an abnormal laboratory finding, for example), symptom, or disease temporally associated with the use of a medicinal product, whether or not considered related to the medicinal product.

All AEs (including serious AEs) will be noted in the study records and on the case report form with a full description including the nature, date and time of onset, determination of non-serious versus serious, intensity (mild, moderate, severe), duration, causality, and outcome of the event.

10.6 Routine Reporting Procedures for All AEs

Grade 2 dose modifying and above AEs will be collected from the time the first dose of study treatment is administered until 30 days following discontinuation of study treatment. Unanticipated problems related to the research involving risks to subjects or others that occur during the course of this study (including Serious Adverse Events (SAEs)) will be reported to the IRB of record in accordance with the IRB of record's SOPs and required timelines. AEs that are not serious but that are notable and could involve risks to subjects will be summarized in narrative or other format and submitted to the IRB at the time of continuing review. External SAEs that are both unexpected and related to the study intervention will be reported promptly after the investigator receives the report per the IRB of record's SOPs.

Care must be taken not to introduce bias when detecting AEs and/or SAEs. Open-ended and non-leading verbal questioning of the subject is the preferred method to inquire about AE occurrence. Appropriate questions include: "How are you feeling?" or, "How does your child seem to feel?" "Have you had any (other) medical problems since your last visit/contact?" or, "Has your child had any (other) medical problems or seem to act differently in any way since his/her last visit/contact?"

Grade 2 dose modifying and above AEs (including serious AEs) will be noted in the study records and on the case report form with a full description including the nature, date and time of onset, determination of non-serious versus serious, intensity (mild, moderate, severe), duration, causality, and outcome of the event.

The severity of toxicities will be graded in accordance with the Common Terminology Criteria for AE (CTCAE) version 5.0. If an adverse event is not covered by one of the

available CTCAE Adverse Event descriptions, and the Investigator deems it medically or clinically significant to document, the applicable “Other” category can be used.

Observed or volunteered AEs Grade 2 attributed to study drug and all Grade 3 and higher AEs, regardless of suspected causal relationship to study drug, will be recorded as AEs in the CRFs.

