3.3 Secondary Objectives

- To assess the duration of response in subjects receiving trametinib at the end of cycles 12 and 24.
- To assess the proportions of subjects with a response at the scheduled protocol visits for disease evaluation at the end of cycles 12 and 24.
- To assess the changes in symptoms and complications/comorbidities associated with Ras/MAPK pathway driven variants in VA.
- Determine the most common and most serious adverse events as defined by Common Terminology Criteria for Adverse Events (CTCAE, version 5.0) in this vascular anomalies population

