10.8 Laboratory and Other Safety Assessment Abnormalities Reported as AEs and SAEs

Laboratory results from non-pediatric institutions or laboratories often have significantly different lab reference ranges, not specific for age. In the event of a greater than $\pm 10\%$ difference in the reference range for a specific lab result, either CHOP or other nationally recognized pediatric standards may be used to determine the grade of the laboratory value.

Any abnormal laboratory test results (hematology, clinical chemistry, or urinalysis), or other safety assessments (e.g., ECGs, radiological scans, vital signs measurements) including those that worsen from screening, and events felt to be clinically significant in the medical and scientific judgment of the investigator are to be recorded as an AE or SAE, in accordance with the definitions provided. In addition, an associated AE or SAE is to be recorded for any laboratory test result or other safety assessment that led to an intervention, including permanent discontinuation of study treatment, dose reduction, and/or dose interruption/delay. However, any clinically significant safety assessments that are associated

with the underlying disease, unless judged by the investigator to be more severe than expected for the subject's condition, are not to be reported as AEs or SAEs.

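### Sections 10.5.2 and 10.6 give three unreconciled rules for which adverse events go on the case report form, so an all-grade ranking of the most common events is not assured

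*Protocol*

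**What the plan says.** Protocol Section 10.5.2 defines an adverse event and then gives a CRF instruction: "All AEs (including serious AEs) will be noted in the study records and on the case report form with a full description". It sets no condition on grade or causality, and no time window.

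Section 10.6, whose heading covers all AEs, is narrower. Its first paragraph says "Grade 2 dose modifying and above AEs will be collected from the time the first dose of study treatment is administered", with collection ending 30 days after treatment stops. Its third paragraph applies the same limit to the CRF: "Grade 2 dose modifying and above AEs (including serious AEs) will be noted in the study records and on the case report form". Its last sentence then names a different set for the CRF: "Observed or volunteered AEs Grade 2 attributed to study drug and all Grade 3 and higher AEs, regardless of suspected causal relationship to study drug".

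Section 10.8 has no grade threshold. It asks for laboratory and other safety findings that the investigator judges clinically significant, and adds that "an associated AE or SAE is to be recorded for any laboratory test result or other safety assessment that led to an intervention", which includes a dose reduction. It excludes findings associated with the underlying disease unless they are more severe than expected.

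Two analyses draw on these data. A secondary objective in Section 3.3 reads "Determine the most common and most serious adverse events as defined by" CTCAE version 5.0, with no grade floor. Section 9.3 makes toxicity the primary safety endpoint, estimated as a rate with an exact 95% confidence interval, and states neither grade nor attribution.

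**The concern.** The three general rules produce three different datasets. A ranking of the most common events is driven by low-grade events, and those are the events on which the rules disagree. Section 2.1.1 names paronychia, diarrhea and rash as the frequent treatment-related effects in the pediatric oncology study, and mild forms of these could be entered at one site and left out at another. With 25 sites, a difference in recorded rates could reflect the sentence followed and not the drug. A statistical analysis plan cannot repair this later, because an event never entered on the CRF cannot be recovered at analysis.

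**Working it through.** **The rules side by side.** Two readings are assumed. Grade 2 dose modifying and above is taken to mean Grade 2 events that are dose-modifying plus all events of Grade 3 or higher. Attributed is taken as possible, probable or definite, as in Section 10.9.

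| Clinical event | 10.5.2 | 10.6, first and third paragraphs | 10.6, last sentence | Rules capturing it |
|---|---|---|---|---|
| Grade 1 | yes | no | no | 1 of 3 |
| Grade 2, not attributed, no dose change | yes | no | no | 1 of 3 |
| Grade 2, attributed, no dose change | yes | no | yes | 2 of 3 |
| Grade 2, attributed, dose-modifying | yes | yes | yes | 3 of 3 |
| Grade 3 or higher | yes | yes | yes | 3 of 3 |

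Section 10.2.1 confines dose-modifying toxicity to events at least possibly attributable to trametinib. The rules are therefore nested: the first 10.6 rule is the narrowest, the last sentence of 10.6 is wider, and 10.5.2 is the widest.

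**Two cases from the protocol.**

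- Grade 2 diarrhea that settles within 72 hours leads to no interruption or dose reduction (Section 10.2.6.7). It is recorded under 10.5.2, recorded under the last sentence of 10.6 if attributed to drug, and not recorded under the first 10.6 rule.
- Grade 1 rash that has not returned to baseline in two weeks leads to a dose reduction (rash table, Section 10.2.6.3). Section 10.2.1.1 counts any dose modification for toxicity as a dose-modifying toxicity, yet a Grade 1 event is below both 10.6 floors. It is recorded under 10.5.2, and arguably under 10.8.

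**The plan's own safety figures.** Section 9.1 gives an 86% chance of at least one toxicity event in 39 subjects at a true rate of 5%: 1 − 0.95^39 = 0.865. It also gives 18% (8% to 34%) for 7 of 39: 7/39 = 17.9%, exact interval 7.5% to 33.5%. Both reproduce. They hold for whatever is counted as a toxicity event, which is the unsettled part.

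**Illustration on assumed inputs.** The protocol gives no grade distribution for this population, so the inputs below are assumptions shown as ranges, and capture through 10.8 is ignored. Suppose an event affects 50% of subjects, 0.5 × 39 = 19.5, each counted once at worst grade. The Grade 1 / Grade 2 / Grade 3+ split runs from 40/45/15% to 80/15/5%. Of Grade 2 events, 60% to 90% are attributed to drug and 20% to 50% are dose-modifying. Expected subjects recorded:

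- 10.5.2: 19.5.
- 10.6, first rule, 19.5 × (Grade 2 share × dose-modifying share + Grade 3+ share): from 19.5 × (0.15 × 0.2 + 0.05) = 1.6 to 19.5 × (0.45 × 0.5 + 0.15) = 7.3.
- 10.6, last sentence, 19.5 × (Grade 2 share × attributed share + Grade 3+ share): from 19.5 × (0.15 × 0.6 + 0.05) = 2.7 to 19.5 × (0.45 × 0.9 + 0.15) = 10.8.

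If toxicity in Section 9.1 is read as all-grade and only a share s of events meets the rule in use, the detection probability is 1 − (1 − 0.05s)^39. This is 70% at s = 0.6, 55% at s = 0.4 and 32% at s = 0.2.

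**The case against.** A reader might infer that the most-common-events objective cannot be answered at all, or that low-grade events are never collected. The documents do not support either. Under 10.5.2 the objective is answered in full. Under the last sentence of 10.6 every drug-attributed Grade 2 event and every Grade 3 or higher event is on the CRF, so a ranking with a floor remains possible. Section 10.8 brings in laboratory and other safety findings at any grade. The synopsis lists physical examination among the safety evaluations, so a Grade 1 rash that led to dose reduction may be recordable through 10.8. Grade 2 rash is also a poor example of lost data: the rash table reduces the dose for it, which makes it dose-modifying and captured even under the narrowest rule.

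Nor do the documents show that sites will in fact diverge. All sites enter data into one database (Section 11.2), and Section 11.4.2 refers to CRF completion guidelines that are not shown and may standardise capture. Divergence is a risk, not an established outcome.

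Primary safety monitoring largely escapes too. The events in Section 9.2 are mostly Grade 3 or 4. The Grade 2 item, pneumonitis, is listed as dose-modifying in Section 10.2.1.1.

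These points limit the reach of the problem without removing it. One might read 10.5.2 as a general definition that 10.6 then refines, but both give CRF instructions in nearly the same words, and 10.6 disagrees with itself: one rule turns on dose modification, the other on attribution.

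**Conclusion.** The inconsistency is real and unresolved in the protocol. It affects Grade 1 clinical events and Grade 2 events without a dose change. Capture from Grade 3 up is secure, so the stopping rule and the most-serious-events part of the objective are essentially unaffected. What is not assured is an all-grade ranking of the most common events and, if toxicity is meant to include all grades, the toxicity rate of Section 9.3. Either could differ between sites. The size cannot be derived from the protocol. On the assumed ranges above, an event affecting 19.5 of 39 subjects would be recorded for 1.6 to 7.3 of them under the narrowest rule and 2.7 to 10.8 under the intermediate one. This rests on the stated reading of the first 10.6 rule and on CRF completion guidelines that could not be seen.

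**What to change.** State one capture rule and use the same words in Section 10.5.2, in all three sentences of 10.6 (first paragraph, third paragraph and last sentence), in 10.8 and in the CRF. Changing only one or two of the 10.6 sentences would leave a contradiction.

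Since the objective has no grade floor, the rule that matches it is all grades regardless of attribution. The collection window from first dose to 30 days after discontinuation should be kept; it appears in 10.6 and not in 10.5.2, so it must survive the edit.

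If a floor is intended, state the same floor everywhere, add that any event of any grade leading to dose modification is recorded, and restrict the most-common-events objective and the toxicity endpoint to that floor.

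The cost is protocol and CRF wording, plus modest extra entry of low-grade events for about 45 subjects if all grades are collected. It should be done before data entry begins or as early as possible, because missed events cannot be restored later.

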10.7 Definition of a Serious Adverse Event (SAE)

An SAE is any adverse drug experience occurring at any dose that results in any of the following outcomes:

- death,
- a life-threatening event (at risk of death at the time of the event),
- requires inpatient hospitalization or prolongation of existing hospitalization,
- a persistent or significant disability/incapacity, or
- a congenital anomaly/birth defect in the offspring of a subject.

Important medical events that may not result in death, be life-threatening, or require hospitalization may be considered a serious adverse drug event when, based upon appropriate medical judgment, they may jeopardize the subject and may require medical or surgical intervention to prevent one of the outcomes listed in this definition.

A distinction should be drawn between serious and severe AEs. A severe AE is a major event of its type. A severe AE does not necessarily need to be considered serious. For example, nausea which persists for several hours may be considered severe nausea, but would not be an SAE. On the other hand, a stroke that results in only a limited degree of disability may be considered a mild stroke, but would be an SAE.

10.8 Laboratory and Other Safety Assessment Abnormalities Reported as AEs and SAEs

Laboratory results from non-pediatric institutions or laboratories often have significantly different lab reference ranges, not specific for age. In the event of a greater than $\pm 10\%$ difference in the reference range for a specific lab result, either CHOP or other nationally recognized pediatric standards may be used to determine the grade of the laboratory value.

Any abnormal laboratory test results (hematology, clinical chemistry, or urinalysis), or other safety assessments (e.g., ECGs, radiological scans, vital signs measurements) including those that worsen from screening, and events felt to be clinically significant in the medical and scientific judgment of the investigator are to be recorded as an AE or SAE, in accordance with the definitions provided. In addition, an associated AE or SAE is to be recorded for any laboratory test result or other safety assessment that led to an intervention, including permanent discontinuation of study treatment, dose reduction, and/or dose interruption/delay. However, any clinically significant safety assessments that are associated

with the underlying disease, unless judged by the investigator to be more severe than expected for the subject's condition, are not to be reported as AEs or SAEs.

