13.1 SAE/SAE Reporting

All SAEs, regardless of attribution or expectedness, must be reported using a FDA MedWatch 3500a Form. For participating sites, this form must be submitted to the coordinating center within 24 hours of learning of the event. Participating sites are required to notify their local IRBs according to institutional reporting policies.

MedWatch 3500a Reporting Guidelines: In addition to completing appropriate subject demographic and suspect medication information, the report should include the following information within the Event Description (section 5) of the MedWatch 3500a form:

- Treatment regimen (dosing frequency, combination therapy)
- Protocol description (and number, if assigned)
- Description of event, severity, treatment, and outcome, if known
- Supportive laboratory results and diagnostics
- Investigator's assessment of the relationship of the adverse event to each investigational product and suspect medication

Follow up information to a safety report should be submitted as soon as the relevant information is available. Additional information may be added to a previously submitted report by any of the following methods:

- Adding to the original MedWatch 3500a report and submitting it as follow-up
- Adding supplemental summary information and submitting it as follow-up with the original MedWatch 3500a form
- Summarizing new information and faxing it with a cover letter including subject identifiers (i.e. D.O.B., initial, subject number), protocol description and number, if assigned, suspect drug, brief adverse event description, and notation that additional or follow-up information is being submitted (The subject identifiers are important so that the new information is added to the correct initial report.)

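### Section 10.8 lets disease-associated safety findings go unreported as AEs or SAEs, with no exception for serious, Grade 3+ or dose-changing findings, and so contradicts 10.5.2, 10.6, 10.9, 13.1 and 13.3

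*Protocol*

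**What the plan says.** Section 10.8 gives three instructions in sequence.

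- Abnormal laboratory results and other safety assessments (ECGs, scans, vital signs), including those that worsen from screening, are recorded as AEs or SAEs.
- An AE or SAE is also recorded for "any laboratory test result or other safety assessment that led to an intervention". Permanent discontinuation, dose reduction and interruption or delay are named as examples.
- The section then makes an exclusion, which opens "However, any clinically significant safety assessments that are associated". The link it has in mind, and the one exception it allows, read "with the underlying disease, unless judged by the investigator to be more severe than expected". The instruction for every finding that falls under it is that they "are not to be reported as AEs or SAEs".

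The other safety sections do not depend on cause.

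- 10.5.2 counts an abnormal laboratory finding as an AE "whether or not considered related to the medicinal product".
- 10.6 says "all Grade 3 and higher AEs, regardless of suspected causal relationship to study drug, will be recorded as AEs in the CRFs".
- 13.1 says "All SAEs, regardless of attribution or expectedness, must be reported using a FDA MedWatch 3500a Form".
- 13.3 sends every SAE to the funding company's patient-safety unit within 24 hours, whatever the cause.
- 10.9 has the investigator name and grade the event first and then assign one of five attribution categories.

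**The concern.** Safety is a primary objective (3.2), and the trial is single-arm and open-label (4.1), so no control group separates drug effects from disease. For the findings it covers, 10.8 makes an unblinded judgement about the disease the test for whether an AE is recorded at all. Elsewhere the protocol treats that judgement as an attribute of an AE already recorded.

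Disease and drug can show in the same tests. Section 10.2.6 lists ejection fraction changes and pneumonitis among its events of special interest. Appendix X grades cardiac and pulmonary disease, and also thrombocytopenia, fibrinogen, liver dysfunction, effusions and the laboratory signs of protein-losing enteropathy. It asks for at least two pertinent criteria, each at Grade 2 or above, before a subject goes on study. Many subjects will thus start with an abnormality in an organ system under safety surveillance, and 10.8 gives no reference point for what severity is expected.

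What is at stake is the completeness of AE and SAE reporting. The DSMB reviews all Grade 4 and 5 AEs and unexpected Grade 3 AEs (11.4.1), and 10.9 allows a possible relationship to be upgraded later. Both depend on an AE entry. With 25 sites (4.7.2) and no stated order of precedence, sites can also differ in what they report.

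**Working it through.** **The plan's own safety figures.** These were checked first, to see whether the problem is arithmetic.

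- Probability of at least one event among 39 at a true rate of 5%: 1 − 0.95^39 = 86.5%. Section 9.1 states 86%.
- Exact (Clopper-Pearson) 95% interval for 7 of 39, i.e. 17.9%: 7.5% to 33.5%. Section 9.1 states 8% to 34%.
- Early-stopping probability from an exact recursion over subjects 5 to 39 with the 9.2 boundaries: 6.0%, 53.4% and 92.3% at true rates of 10%, 20% and 30%. Section 9.2 states 5%, 55% and 91% from simulation, and each differs by less than 2 points.
- The 9.2 boundary table matches its rule (lower limit of the two-sided exact 95% interval above 10%) at every number of subjects from 5 to 39.

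The figures are sound. The point concerns which findings become AEs.

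**The rules side by side.** Take a laboratory, ECG, imaging or vital-sign finding that the investigator considers disease-associated and no worse than expected.

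1. *It is Grade 3 or higher.* 10.5.2 makes it an AE and 10.6 has it recorded whatever the cause. 10.8 says it is not reported.
2. *It meets a seriousness criterion in 10.7, such as hospitalization.* 13.1 and 13.3 require it to be reported whatever the attribution, expectedness or cause. 10.8 expressly names SAEs among what is not reported.
3. *It led to a dose reduction, interruption or discontinuation.* The preceding sentence of 10.8 requires an AE or SAE. The exclusion then opens with a word of contrast and makes no exception for such findings.
4. *The disease is a plausible explanation.* 10.9 has a place for this case: its unlikely category covers abnormal laboratory results for which underlying disease offers a plausible explanation. That presumes the event has been recorded and then attributed. Under 10.8 it never reaches attribution.

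In each case two current instructions give opposite answers, and no section ranks them.

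**Limits of the conflict.** The exclusion covers safety assessments only, so a purely clinical AE is outside it. It does not apply when the investigator judges the finding worse than expected. Sections 10.2.6.5 and 10.2.6.8 have their own SAE instructions for symptomatic or unrecovered LVEF decline and for diagnosed retinal vein occlusion or retinal pigment epithelial detachment, none with a disease exception. For those events the more specific rule can reasonably be read to govern.

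**The case against.** The best defence is that 10.8 has an evident purpose. The trial enrols subjects with Kaposiform lymphangiomatosis who have baseline coagulopathy and thrombocytopenia, and it expects low albumin. Reporting every such value as an AE would swamp the safety data. That stands for findings that are non-serious and lower-grade. It does not explain why SAEs are named in the exclusion.

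A second defence is that 10.8 decides what becomes an AE, so that 10.6 and 13.1 apply only to what remains. But 10.8 is worded as a reporting rule, and 10.5.2 has already defined an AE without regard to cause.

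Third, 10.2.1 defines dose-modification toxicity as at least possibly attributable to trametinib, which narrows the dose-change conflict. It does not remove it. Section 10.1.2 also allows interruption for other medically relevant reasons, and the possible category in 10.9 expressly allows the subject's clinical condition to contribute, so one finding can be both possibly drug-related and disease-associated.

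A reader might infer three stronger conclusions that the documents do not support.

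- *That the primary toxicity rate is biased downward by a stated amount*, for instance by removing events from the protocol's example of 7 in 39. The safety endpoint is toxicity of trametinib (9.3), and 9.2 counts only treatment-associated severe toxicity. An event ascribed wholly to the disease would not count under 9.2 even if recorded, and 9.3 does not say that it would count as trametinib toxicity. The document also gives no share of findings that would be so ascribed. Subtracting events from the 7 does not measure this defect.
- *That all toxicity resembling the disease is lost.* The exception for unexpectedly severe findings, the restriction to safety assessments and the event-specific SAE rules all limit the exclusion.
- *That the data are deleted.* Scheduled tests continue, their results stay in source documents, and site data go into the study database. What is missing is the AE or SAE entry, with the review and reporting that it triggers.

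**Conclusion.** The contradiction is real. If 10.8 is followed as written, a serious or Grade 3+ laboratory, ECG, imaging or vital-sign finding can be absent from AE and SAE tabulations, expedited reporting and DSMB review, and it cannot be re-attributed later as an AE. This depends on the investigator judging it disease-associated and no worse than expected.

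No numerical effect can be given. How often the exclusion would be used is not in the document, and its effect on the treatment-associated toxicity rate and the 9.2 stopping probabilities is not quantifiable. The safety figures in 9.1 and 9.2 need no correction on this account.

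The point should be settled in the protocol because it governs what sites enter, and an analysis plan cannot tabulate AEs that were never recorded. It is worth correcting because safety is a primary objective without a control group and the remedy is small.

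**What to change.** Add one sentence to 10.8. It should state that the disease-associated exclusion does not apply to SAEs, to Grade 3 or higher findings, or to findings that led to dose reduction, interruption or discontinuation. It should add that these are recorded and reported under 10.6, 13.1 and 13.3 with a 10.9 attribution category. The investigator's view that the disease is the cause is then kept as an attribution and can be reviewed.

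Keep the exclusion for other non-serious, lower-grade findings expected from the disease, so that sites are spared routine entries for known abnormalities.

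The cost is some extra CRF entries and somewhat higher all-cause AE rates. No treatment or dose rule changes.
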